## **10.0 Data and Specimen Banking**

The Early Psychosis data repository will be used to store demographic and clinical information collected from consenting participants who agree to have their information stored in the data repository. This centralized database will store information for future unspecified use. In doing so, this will allow for a less burdensome and more efficient process for collecting information routinely utilized by all researchers. Consent for data to be included in the repository will be obtained during the consent process. Data will be stored for 20 years at which time the electronic repository and the database will be cleared. Re-consent will be attempted in person when those who already consented return for follow-up visits, if we can do so. For those that we can't meet in person, we will re-consent by phone. Those who cannot be contacted, either in person or by phone will be flagged in the repository and data for these individuals will only be kept for 10 years.

The data from the process evaluation will NOT be stored in the Early Psychosis Repository.

## **11.0 Data and Specimen Management**

**11.1** *Describe the data analysis plan, including any statistical procedures.* The goals of this study are to (1) measure DUP and perceptions regarding barriers to care and shared-decision making, and (2) conduct a process evaluation of the implementation of the PQ-B (a screening tool to identify risk of psychosis) at SHAC. Descriptive statistics (e.g., means, standard deviations, medians, quartiles) and summary statistics (for the process evaluation) statistics (will be calculated to summarize the characteristics of the student population, to summarize instrument scores, and to summarize process data regarding the PQ-B at an aggregate level . DUP among those with FEP and duration of

PROTOCOL TITLE: Duration of Untreated Psychosis and Perceived Barriers to Mental Health Care Among College Students

attenuated symptoms among those with CHR will be reported in days as a mean and 95% exact Poisson CIs. We will report the mean BSPHS summed scores and 95% CIs.

*11.2 Provide a power analysis, if necessary.* Not Applicable

*11.3 Steps that will be taken to secure the data to maintain confidentiality during storage, use, and transmission.* To assure confidentiality all study personnel will be trained and certified in basic human subject's research protections by the UNM HSC CITI Training Program. In addition, the PI will administer ongoing training and supervision of the research coordinator to assure confidentiality and privacy for participants and participant data. Hard copies of the consent will be separated from any hard copies of data and will be stored in a locked file cabinet in the Research Coordinator's office located in the UNM's Department of Psychiatry and Behavioral Sciences, Division of Community Behavioral Health (CBH). CBH is located at [name]. The PI also has an office at CBH. Only the PI and research coordinator will have keys to the locked file cabinet. Paper records may be kept for five years following the conclusion of the research. In addition, study records of minors (less than 18 years old) enrolled into the study will be retained until they turn 22 years old. Eventually, copies of the consents and contact information will be scanned and stored on the University's secure O drive, under the Psychiatry folder for an additional five years at which time the information will be permanently deleted. The O drive is a domain share (health.unm.edu) that is setup between groups and users within this domain. Security for the O drive is controlled by login for the domain, with a username and password. Access to the O drive is controlled by UNM admins. As hardcopy data are collected, the research coordinator will transcribe the raw data to an electronic REDCap database. Data may also be collected directly via tablet into REDCAP databases. All REDCAP databases will be password protected and only the PI and research coordinator will have access to the data. Participants will be assigned a participant ID number at the first stage of data processing. The participant ID number will be written at the top of paper symptom scales and only participant ID numbers will be entered into the electronic databases. Data will never be directly linked to participant identifying data. An electronic Access database with links between participant identifying information and ID numbers will be kept on the secure UNM HSC O-drive. Only research personnel will have access to those links.

The limited data set will be shared and stored on a shared drive created by HSC IT. The shared drive is located under the secure Psychiatry O: drive. Only [name], [name], [name] and [name] have access to this shared drive. The limited data set excel sheet will also be password protected.

[name] will be responsible for assigning a unique identifier to every student who received a SIPS assessment and did not qualify for enrollment and this unique identifier will be entered into the excel spreadsheet that will be shared with the research team. The limited data set will be shared and stored on a shared drive created by HSC IT. The shared drive is located under the secure Psychiatry O: drive. Only research team members will have access to this shared drive. The limited data set excel sheet is also password protected.

The final merged limited dataset created by the honest broker will be housed under the secure Psychiatry O:drive in a password protected excel sheet. Only the research team will have access to the final dataset.

PROTOCOL TITLE: Duration of Untreated Psychosis and Perceived Barriers to Mental Health Care Among College Students

*11.4 Procedures that will be used for quality control of collected data:* Double entry data transcription will be used when data are transcribed from paper-and-pencil forms to the electronic REDCap database. Standard REDCap data backup and data protections will be used during the electronic data storage phase.

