## 1.0 Objectives

Increased duration of untreated psychosis (DUP), defined as the time from manifestation of the first psychotic symptom(s) to initiation of evidence-based treatment, is associated with poorer clinical and functional outcomes (Fusar-Poli et al., 2009). Factors associated with longer DUP include perceived barriers to care among those experiencing psychotic-like symptoms and feelings of not being listened to or not being offered the opportunity to make decisions regarding treatment (referred to as shared-decision making). The primary objective of our proposed study is to investigate the association between DUP and perceptions regarding barriers to care and shared-decision making among college students. The secondary objective is to conduct a process evaluation of the inclusion of a screening tool (the Prodromal Questionnaire Brief- PQ-B developed by Loewy et al., 2011) during triage at University of New Mexico Student Health and Counseling Center (SHAC). SHAC implemented the PQ-B August 1st, 2020 to improve quality of clinical services by identifying students at risk of first episode psychosis (FEP) and referring those identified at high risk to coordinated specialty care programs (i.e., Early and CONNECT) in the Department of Psychiatry and Behavioral Sciences, University of New Mexico. The Early Program is a coordinated specialty care program for the young adults experiencing first episode psychosis (FEP) while the CONNECT program provides stepped care to young individuals at clinical high risk (CHR) of developing psychosis.

The specific aims are to:

1. Measure DUP among University of New Mexico (UNM) college students enrolled in the Early or CONNECT Programs in the Department of Psychiatry and Behavioral Sciences and identify other factors that may contribute to longer DUP, such as perceptions relating to barriers to mental health care and shared decision-making. We hypothesize that there will be: (1) a positive association between DUP and the number of perceived barriers to care, and (2) a negative association between DUP and feelings of shared-decision making.

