**2.3. Contribution to the Literature.** Upon successful completion of the proposed research, we expect our contribution to the literature to be preliminary data on DUP among college students and perceptions regarding barriers to receiving mental health care and shared-decision making.

The quality improvement data will also contribute to the literature on screening for first episode psychosis among a college population.

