## **8.0 Study Endpoints**

*8.1 Primary and secondary study endpoints.* This is not an outcome study, data will only be collected at one time-point, which will be immediately following the consent process.

*8.2 Primary or secondary safety endpoints.* NA

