## 9.0 Procedures Involved

9.1 *Overview of the study design.* The study will use a correlational research design in which we will collect data for each participant only once.

*Overview of research procedures being performed and when they are performed.* Participants will be recruited among UNM college students and who are determined eligible for the proposed study (see inclusion criteria Section 3.2). Once determined eligible, individuals will be invited to participate in the research. Those who agree to participate will complete the consent process. The research coordinator ([name]) or PI ([name]) will be responsible for consenting the individual and data collection. Data will be collected through completion of standardized tools that have all been determined to be reliable, valid and appropriate for the study population (described in 9.3). Data will be collected either through (i) face to face interviews, (ii) phone, or (iii) HIPAA Compliant Zoom Account. These last two options have been put in place to accommodate the social distancing and public health stay at home orders that have been put in place by the NM Governor during COVID. Data will be collected after the consent process. We will aim to collect data at one point in time. However, due to the illness associated with the target population, we may need to split the interview over two time periods. Participants will be provided with a \$20.00 amazon merchandise card per hour to standardized compensation across participants. We will always round up. For example: if a participant completes the surveys in 45 minutes we will give them a \$20.00 merchandise card; if a participant completes the surveys in an hour and a half we will give them two \$20.00 merchandise cards.

9.2 *What data will be collected, including long-term follow-up.* This is not an outcome study so no long-term follow-up data will be collected. Data will only be collected at one-point, following the consent process. In addition to the SIPS, which will be completed by clinicians during the determination of eligibility process, participants will complete the instruments listed below. Noteworthy, is that during the consent process, we will ask students their permission to use their data collected during the determination of eligibility process as well as data from other standard clinical assessments that were conducted on intake. The following instruments will take approximately 2-3 hours to complete.

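### The primary objective is the association of DUP with perceived barriers and with shared decision-making, but section 11.1 plans only one-variable summaries and so estimates neither association

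*Combined protocol and SAP*

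**What the plan says.** Section 1.0 gives the primary objective as to "investigate the association between DUP and perceptions regarding barriers to care and shared-decision making among college students". Aim 1 turns this into two directional hypotheses: "a positive association between DUP and the number of perceived barriers to care" and "a negative association between DUP and feelings of shared-decision making". The population named in aim 1 is UNM "college students enrolled in the Early or CONNECT Programs in the Department of Psychiatry and Behavioral Sciences", so it takes in both first-episode psychosis (FEP) and clinical-high-risk (CHR) students.

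Section 9.1 describes the approach in one phrase: "The study will use a correlational research design". It does not say what will be correlated with what, or how.

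Section 11.1 is the only place where analyses are specified. Its first goal reads "1) measure DUP and perceptions regarding barriers to care and shared-decision making"; the word association no longer appears. The planned outputs are:
- descriptive statistics for the student population, the instrument scores and the PQ-B process data;
- mean DUP in FEP and mean duration of attenuated symptoms in CHR, in days, with exact Poisson 95% CIs;
- the mean summed BSPHS score with a 95% CI.

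Section 11.2 marks a power analysis as not applicable. Section 22.0 expects about 40 students and gives no FEP/CHR split.

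**The concern.** A mean duration and a mean score, each with its interval, say nothing about whether students with longer delays report more barriers or less shared decision-making. A team that carried out section 11.1 to the letter could neither support nor contradict either primary hypothesis.

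In practice someone will probably add a correlation at the end. Without a written rule, the statistic, the group and the scores would then be chosen with the data in hand. The risk is not hypothetical. The honest-broker text in section 9.2 reports 21 participants already enrolled in the research arm through PQ-B screening, and section 7.3 expects analysis to run throughout the study. In groups this small, such choices could change the result.

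**Working it through.** **1. Objective against plan**

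| Needed by section 1.0 | Planned in section 11.1 | Relates two variables? |
|---|---|---|
| DUP with perceived barriers (hypothesis 1) | Mean duration with CI; mean BSPHS with CI | No |
| DUP with shared decision-making (hypothesis 2) | Mean duration with CI; CollaboRATE only as one of the instrument scores to be summarised | No |

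Planned estimates of the hypothesised associations: 0 of 2. A search of the whole document for a correlation coefficient, regression, test or model linking duration to either scale finds none. The database merge described in section 9.2 serves the PQ-B evaluation and does not fill the gap.

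**2. Can the planned outputs carry the answer indirectly?** No. As a check of the logic, with invented data, 40 lognormal durations and 40 normal scores were generated and only the pairing was changed. The one-variable summaries were identical each time (duration mean 224.1, median 160.0; score mean 48.54, SD 7.44). The Spearman correlation was +1.00 when both were sorted the same way, -1.00 when one was reversed, and 0.07 after a random shuffle. One set of planned outputs is compatible with any association.

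**3. What an added correlation could deliver.** The plan has no figure to reproduce: the 40 in section 22.0 comes without effect size, alpha or power. For illustration, take an observed Spearman correlation of r = 0.30 (an assumption; signs reverse for hypothesis 2) and the usual approximate 95% CI:

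tanh( atanh(r) ± 1.96 × sqrt( (1 + r²/2) / (n − 3) ) )

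Here atanh(0.30) = 0.3095 and 1 + 0.30²/2 = 1.045.

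- n = 40 (every student in one group, the best case): 1.96 × sqrt(1.045/37) = 0.329. Limits tanh(-0.020) to tanh(0.639), that is -0.02 to 0.56.
- n = 20 (an assumed even split): 1.96 × sqrt(1.045/17) = 0.486. Limits tanh(-0.176) to tanh(0.795), that is -0.17 to 0.66.

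The n = 40 line is only a bound. Section 11.1 already treats DUP in FEP and attenuated-symptom duration in CHR as different quantities, so they should not be pooled.

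**The case against.** The best defence is that section 9.1 is part of the plan too. It declares the design correlational, so the class of analysis is known and only the estimator is missing. Section 2.3 promises only "our contribution to the literature to be preliminary data on DUP among college students", and section 8.1 says "This is not an outcome study, data will only be collected at one time-point". For a single-visit, minimal-risk survey of about 40 students, a light analysis plan may be proportionate.

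Part of this stands. The design label shows that association was intended, so the gap looks like an omission in writing. A reader might infer that the study has abandoned its primary question; the documents do not support that. But the label names no statistic, group or score, and neither the modest ambition nor the single time-point withdraws the objective or the hypotheses.

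The defence also rules out several stronger readings:
- **CollaboRATE will not be analysed.** Section 11.1 does not name it, but its general commitment to summarise instrument scores covers it.
- **The population for the hypotheses is undefined.** Section 1.0 dates DUP from the first psychotic symptoms, section 9.2 says CHR participants have by definition had no psychotic episode, and section 11.1 reports DUP for FEP only. These definitions already point to FEP. Only the wording of aim 1, which measures DUP across both programs, needs clarifying.
- **CollaboRATE has no scoring rule.** Section 9.2 states none, but the instrument is attachment #4, which is not in the text reviewed, and the rule may be there. Section 9.2 also indicates a graded score. With complete items, a sum and a mean give the same Spearman value.
- **The missing power analysis is an error.** For a study promising preliminary data, adding precision figures to section 11.2 is a preference, not a correction.

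**Conclusion.** The concern holds: the analysis planned in section 11.1 does not match the primary objective in section 1.0, and neither of the two hypothesised associations would be estimated. This conclusion rests on the text alone and on no assumed number. It is more than missing detail, because the listed outputs cannot answer the primary question at all.

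The interval widths are illustrative. They depend on the assumed correlation of 0.30 and on group sizes that the protocol does not give. They show that an added analysis would yield imprecise, preliminary estimates. They do not show that the study is not worth doing.

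**What to change.** Add to section 11.1:

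> For hypotheses 1 and 2 we will estimate the Spearman correlation, with 95% CI, of DUP with the BSPHS summed score and with the CollaboRATE total (sum of the three items, unless attachment #4 specifies another rule) among FEP participants. The same correlations, using duration of attenuated symptoms, will be reported separately for CHR participants as a supporting analysis. The two durations will not be pooled as one variable.

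State also that the number of perceived barriers in hypothesis 1 is measured by the BSPHS summed score, since section 9.2 gives a sum of Likert items and not a count.

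Date the addition and record whether any duration-by-score data had already been examined. If they had, label the correlations post hoc.

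Alternatively, if only description is intended, restate the objective and hypotheses in section 1.0 as descriptive.

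The cost is one paragraph, one clarifying sentence and a dated note. Duration, BSPHS and CollaboRATE are already collected under section 9.2. The drawback is wide intervals, so the results should be presented as preliminary estimates. If the data have already been looked at, full prespecification cannot be recovered.

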## 2.0 Background

2.1 General Background. Clinical and general population studies on FEP have generated enough evidence to have confidence in three issues. First, the DUP is a strong predictor of outcome, such that current clinical recommendations are <3-6 months

PROTOCOL TITLE: Duration of Untreated Psychosis and Perceived Barriers to Mental Health Care Among College Students

(Compton et al., 2008). Second, in the U.S., individuals are still presenting with DUP on average of two years (Marshall et al., 2005). Third, the reasons for treatment delay are multiple and complex (Apelodoorn et al., 2014). Various classifications have been developed to categorize the factors that contribute to an extended DUP. Compton and Broussard (2011) for example, identified six categories, including: (i) demographic, (ii) premorbid and onset-related, (iii) illness-related, (iv) family-level, (v) societal, and (vi) health system and service level factors.

With the first symptoms of psychosis being most likely to surface around ages 15 to 24, college age young adults are at increased risk of FEP and CHR of psychosis (Kessler et al., 2007; Simon et al., 2017). Studies on the course of schizophrenia indicate that the initial onset of the disorder shows a steep increase during adolescence and young adulthood and then begins to decrease around the age of 25 (Hafner et al., 1993; Sham et al., 1994). Simon et al., (2017) reported a FEP incidence rate of 86 per 100,000 among ages 15-29 compared to 46 per 100,000 among 30-59 across a variety of care settings. There are other environmental risk factors unique to college students that may increase risk of psychosis and contribute to increased DUP. First, attending college can be a stressful time for many students, learning to live independently and handle college level work load. Second, there are higher rates of illicit and prescription drug use among college students. Third, lack of identification of mental health symptoms and/or treatment have surfaced as system-level challenges on college campuses. This contributes to the persistence of mental health problems among students, partly due to the under-resourcing of college mental health services in relationship to needs. Lastly, many college students are in the process of transitioning between adolescence to adulthood and may be less likely to recognize when to seek help or to feel comfortable with accessing services independent of family support.

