***3.2 Inclusion and Exclusion Criteria.*** Eligible participants included in the study will be: (1) 15-30 year-old UNM college students who present to the UNM Early Program or the UNM CONNECT program for an intake, (2) who screen positive for clinical high risk or FEP, and (3) agree to participate in the study. Participants will be excluded if: (1) they are below the age of 15 years old or above the age of 30, (2) are not UNM college students, (3) screen negative for clinical high risk or FEP, (4) refuse to participate in the study, and/or (5) are cognitively unable to provide informed consent as demonstrated by a brief cognitive screen prior to completion of the enrollment interview. Cognitive capacity to consent to research participation will be assessed by the research coordinator using the form included in Attachment 1 - *Evaluation to Sign an Informed Consent Document for Research*.

There are no exclusion or inclusion criteria specific to the PQ-B screening tool implemented at SHAC. The triage process at SHAC has included universal screens for depression, anxiety and substance use for years. As of August 1st, 2020, SHAC extended the universal screening to include risk of psychosis through the inclusion of the PQ-B. Universal screening means that all students who seek counseling services at SHAC complete the PQ-B at triage.

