**Demographic Data:** Basic demographic data will be collected on each participant, including city of birth, phone number and email (for future contact), current education year, date of birth, sex, gender, race and ethnicity. City of birth and full date of birth are required to obtain a Global Unique Identifier (GUID) in the NIMH Data Archive. A GUID is a subject ID allowing researchers to share data specific to a study participant without exposing personally identifiable information. A copy of the demographic form has been attached.

**Structured Clinical Interview for DSM-5 (SCID-5)** (First et al., 2015). The SCID-5 Research Version will be used to confirm clinical diagnoses for all participants enrolled in the research study. Only the sub-units for psychosis, mood disorders, substance abuse and trauma-related disorders will be completed. The SCID-5 will be administered by the research coordinator who has been trained in its use and achieved sufficient reliability for research purposes.

**Duration of Untreated Psychosis (DUP)** will be collected using the Circumstances of Onset and Relapse Schedule (CORS) (Norman and Malla, 2002). The CORS includes

**PROTOCOL TITLE:** Duration of Untreated Psychosis and Perceived Barriers to Mental Health Care Among College Students

the Topography of Psychotic Episode (TOPE), which together traces the process of seeking treatment by identifying step-by-step contacts with medical and mental health services in the pathway toward contact with early psychosis services. The CORS protocol includes specific questions and follow-up prompts to help determine the onset of prodromal and psychotic symptoms and pathways to care (Attachment 2). The CORS has well established psychometric properties and takes approximately an hour to complete. It will be completed by the Research Coordinator or PI through semi-structured interviews. While participants identified as at CHR for psychosis, by definition, would not yet have had a psychotic episode, we will similarly record onset of attenuated psychosis symptoms in order to better understand barriers and pathways to care for this group.

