for a secondary screen we will not be able to determine whether the Prodromal Questionnaire-Brief (PQ-B) is an appropriate psychosis screening tool among a college population (a primary goal of this research).

The third excel file includes 21 participants who were enrolled in the research arm of this study through the PQ-B screening. Nine of these 21 participants did not sign an ROI at SHAC to allow access to their PQ-B scores. This is a critical piece of data we need in order to get a full picture of how this screening tool identifies individuals at risk for psychosis.

To address this limitation, we are proposing to use an honest broker process to merge all three databases to allow us to fully understand what PQ-B scores indicate clinically within this population. An honest broker is an IRB recommended practice for merging data. We have identified [name] (statistician and Department of Psychiatry and Behavioral Sciences faculty member) to serve as the honest broker.

Using the master key with client names and unique identifiers for records in the triage limited database, the honest broker will be responsible for merging the three excel files to create a complete dataset. Once completed, the final merged limited dataset-containing both initial screening information from SHAC, secondary screening information from Psychiatry and research data- will be stripped of any identifying information and returned to the study team.

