## **22.0 Number of Subjects**

We expect to enroll approximately 40 students into the study over the study period.

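### Does Section 11.1 need a planned summary by entry route beside the DUP and barriers figures?

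*Combined protocol and SAP*

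**What the plan says.** Section 11.1 gives the analysis plan in a few sentences. Descriptive statistics will be used "to summarize the characteristics of the student population, to summarize instrument scores, and to summarize process data regarding the PQ-B". DUP in the FEP group and duration of attenuated symptoms in the CHR group are each to be reported as a mean in days with an interval, and BSPHS as a mean with a 95% CI. FEP versus CHR is the only split named. Section 11.2 gives no power analysis.

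Section 9.2 describes the CORS as "identifying step-by-step contacts with medical and mental health services in the pathway toward contact with early psychosis services". For CHR participants it adds that "we will similarly record onset of attenuated psychosis symptoms in order to better understand barriers and pathways to care for this group". The same section refers to a file of "21 participants who were enrolled in the research arm of this study through the PQ-B screening".

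Aim 1 in Section 1.0 includes the intention to "identify other factors that may contribute to longer DUP". Section 2.1 cites a six-part classification of causes of delay, one part being "health system and service level factors". Section 3.2 admits "UNM college students who present to the UNM Early Program or the UNM CONNECT program for an intake", without requiring a counseling-center referral. Section 22.0 says "We expect to enroll approximately 40 students into the study over the study period".

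**The concern.** The study collects pathway information in an interview of about an hour, gives pathways as one reason for collecting it in the CHR group, and then names no pathway summary in the analysis plan. Eligibility is open to students who arrive by any route, so the sample could mix students picked up by PQ-B screening at the counseling center with students who came another way.

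If the two kinds of student differ in duration or in perceived barriers, the overall means depend partly on the mix. If everyone came through screening, the figures describe students found at a center that screens, and a reader would want to know that too. Without a count by route a reader cannot tell which applies. What is at stake is how far the DUP and BSPHS summaries can be generalized. The summaries would still be correct for the sample enrolled.

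**Working it through.** **1. Is a route summary excluded, or only unnamed?** Section 11.1 covers the characteristics of the student population in general terms and lists no variables. Entry route is such a characteristic. The CORS is one of the study instruments, and its record of contacts supplies the variable. For the 21 screened participants, route is known already. Nine of them signed no release of information, but that blocks access to their PQ-B scores and does not hide how they entered. The count is unnamed, not excluded, and needs no new data.

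**2. Do the other passages promise a route analysis?**
- Aim 1 gives its own examples of other factors: perceived barriers and shared decision-making. These are measured by BSPHS and CollaboRATE. Entry route is not among them.
- The service-level category in Section 2.1 comes from a cited classification given as background.
- The CHR sentence in Section 9.2 explains why symptom onset is recorded in people who have had no psychotic episode. It does not commit to comparing recruitment sources.

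**3. Can the effect of mix on an overall mean be sized?** Let N be the total enrolled, with 21 through screening. Then

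overall mean − screened-only mean = (1 − 21/N) × (other-route mean − screened mean).

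- N = 21: factor 1 − 21/21 = 0.
- N = 30 (assumed): factor 1 − 21/30 = 0.30.
- N = 40 (the planned figure, not an achieved one): factor 1 − 21/40 = 0.475.

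The factor lies between 0 and 0.475 over this range. The second term, the gap between routes, appears nowhere in the documents, so no figure in days can be supported. DUP also applies only to FEP, and the FEP/CHR split of the 21 is not given, so the factor for DUP itself is unknown.

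**4. What would a breakdown by route show?** The 95% half-width for a difference in means, in SD units, is 1.96 × √(1/21 + 1/(N − 21)).

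| Assumed N | Screened / other | Half-width (SD) |
|---|---|---|
| 25 | 21 / 4 | 1.07 |
| 30 | 21 / 9 | 0.78 |
| 40 | 21 / 19 | 0.62 |

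Within FEP the cells are smaller. Using t(0.975, a + b − 2) × √(1/a + 1/b) with assumed cells of 5/5, 10/10 and 16/14, the half-widths are 1.46, 0.94 and 0.75 SD. Such a table could describe the groups but could not establish or rule out a moderate difference. Its smallest cells might have to be suppressed for privacy.

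**5. Do the planned summaries depend on route being reported?** No. The FEP, CHR and BSPHS means describe the enrolled students whatever their route. Whether the stated interval method suits a mean in days is a separate question, and route has no bearing on it.

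**The case for a change.** The best case for a change is that it costs one sentence and tells readers whom the figures describe. Section 2.1 cites a study in which screening everyone found three times the prevalence of at-risk states seen in a population referred on clinical concern, so route can alter case mix. Section 2.3 presents the results as preliminary data on DUP among college students, which makes the source of those students relevant. The process evaluation does not fill the gap. It counts completed PQ-Bs, positive screens and referrals, and the three-file merge is meant to explain PQ-B scores. Neither is tied to DUP or BSPHS.

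Much of this stands. The omission is real, and a count by route would help a reader. But the cited study concerns who is detected, not how long they were untreated or what barriers they perceived. The argument also needs a second route in use and a difference between routes, and the documents show neither. What remains is a sensible line in a baseline table. The CORS interview is the safer source for it, because the third file is described only by its screened participants and may not identify anyone else.

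**Conclusion.** No change to the plan is needed. Section 11.1 leaves entry route unspecified, but its general wording permits the count, and an analyst describing this sample would be expected to give it beside the duration and BSPHS figures. This is optional reporting detail; no planned estimate is wrong without it.

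The size of any mix effect cannot be stated. It is zero if all participants came through screening or if the routes do not differ; otherwise it is at most 0.475 of an undocumented gap if enrollment reached 40. A comparison by route would carry a half-width of about 0.62 SD or more for totals up to 40, so prespecifying one would gain little. These figures assume that the 21 are all the screened entrants and that the total lies between 21 and 40; the documents confirm neither. That Section 11.1 sets out no analysis of the associations hypothesized in aim 1 is a separate and larger matter, and this conclusion does not bear on it.
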